## 6.5. Data handling convention

### 6.5.1. Visit Time Windows

For ITT and safety by-visit analyses, all follow-up visits or the exit visit, participants will be reassigned with the visit number based on the number of days from the first dose date according to the following windows corresponding to relevant analysis.

Analysis Phase	Analysis Visit (Derived)	Study Visit (eCRF)	Statistical Analyses Window
Pretreatment	Baseline	Day 1 (Visit 1)	Treatment Day $\leq$ 1, pre-dose/randomization
Treatment	Day 1	Day 1 (Visit 1)	Treatment Day 1, post dose/randomization
	Day 3	Day 3 (Visit 2)	Treatment Day [2, 4]
	Day 7	Day 7 (Visit 3)	Treatment Day [5, 10]

AGN-190584

Analysis Phase	Analysis Visit (Derived)	Study Visit (eCRF)	Statistical Analyses Window
	Day 14	Day 14 (Visit 4)	Treatment Day [11, 21]
	Day 30	Day 30 (Visit 5)	Treatment Day [22, 45]

If multiple assessments were taken within an analysis window, the assessment obtained on the day closest to the target day will be used; in the case of a tie, the assessment obtained on the later day will be used in the analysis.

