8.3.3. Follow-up of Adverse Events and Serious Adverse Events

After the initial AE/SAE report, the investigator is required to proactively follow each participant at subsequent visits/contacts. All AEs/SAEs will be followed until resolution, stabilization, the event is otherwise explained, or the participant is lost to follow-up (as defined in Section 7.3).

The investigator is obligated to perform or arrange for the conduct of supplemental measurements and/or evaluations as medically indicated or as requested by Allergan to elucidate the nature and/or causality of the AE or SAE as fully as possible. This may include additional laboratory tests or investigations, histopathological examinations, or consultation with other health care professionals.

If a participant dies during participation in the study, the investigator will provide Allergan with a copy of any postmortem findings including histopathology.

If a participant is hospitalized and discharged, follow-up attempts must be made to obtain the discharge summary from the hospital and, if obtained, it should be sent to the sponsor.

New or updated information will be recorded in the originally completed eCRF.

The investigator will submit any updated SAE data to Allergan within 24 hours of receipt of the information.

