**5.6.8. Intraocular Pressure**

IOP is measured for each eye using the Goldmann applanation tonometer at each visit. Tabulations will be based on the worst change (greater increase from baseline) between 2 eyes assessed at each visit. Descriptive statistics for IOP and changes from baseline at each assessment timepoint will be presented by treatment group.

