**5.6.9. Slit Lamp Biomicroscopy**

Biomicroscopy will be performed in each eye at each visit, by slit lamp examination, without pupil dilation, including but not limited to lids/lashes, conjunctiva, cornea, and anterior chamber. Observations for the examination will be graded on a 5-point scale (0=none, 0.5=trace, 1=mild, 2=moderate, 3=severe) except for the anterior chamber (in cells: 0=0 cells, +0.5=1-5 cells, +1=6-15 cells, +2=16-25 cells, +3=26-50 cells, and +4=>50 cells; in flare: 0=none, +1=faint, +2=moderate, +3= marked and +4=intense).

The number and percentage of participants with clinically significant biomicroscopy findings will be tabulated by finding category, assessment timepoint and treatment group. A clinically significant finding is defined as more than one severity grade increase (worsening) from baseline in one or both eyes. If a pathology is recorded at a follow-up visit but not at baseline, the baseline will be imputed with the same pathology, with a grade of zero (none).

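### The specified IOP and biomicroscopy summaries use one exam per visit window, so some early-exit exams and most unscheduled exams do not enter them

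*SAP*

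**What the plan says.** SAP 6.5.1 sets the scope of the windows: "For ITT and safety by-visit analyses, all follow-up visits or the exit visit, participants will be reassigned with the visit number". The windows are Days 2 to 4, 5 to 10, 11 to 21 and 22 to 45, for target Days 3, 7, 14 and 30, with no gap between them. Where a window holds more than one exam, the rule is that "the assessment obtained on the day closest to the target day will be used". A tie goes to the later exam. There is no exception for safety, and unscheduled exams are not mentioned.

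For IOP, SAP 5.6.8 says "Descriptive statistics for IOP and changes from baseline at each assessment timepoint will be presented by treatment group". The worst change it refers to is the worse of the two eyes at one visit, not the worst across visits. In SAP 5.6.9, participants with a clinically significant biomicroscopy finding (worsening by more than one grade from baseline in either eye) are "tabulated by finding category, assessment timepoint and treatment group". The visible SAP gives no any-time, maximum post-baseline or last-on-treatment summary for either measure.

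**The concern.** A nearest-day rule is ordinary for by-visit means. The difficulty is that by-visit output is the only output the SAP specifies for these two measures. An exam that loses the selection therefore has no other specified summary of IOP or biomicroscopy to appear in.

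The exams that can lose include those made off schedule for a reason. Protocol 8.3.3 obliges the investigator to "perform or arrange for the conduct of supplemental measurements and/or evaluations as medically indicated" to clarify an AE, and Protocol 7.1 and 7.2 provide for data collection at early exit. Suppose a participant is seen on Day 7 and exits on Day 9. Both exams fall in Days 5 to 10, the Day 7 exam is on target, and the Day 9 exam is not used. If Day 9 was the only exam with a two-grade worsening or a raised IOP, that value enters neither the count of clinically significant findings nor the reported IOP maximum.

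**Working it through.** **Inputs.** The windows, targets, nearest-day rule and tie rule come from SAP 6.5.1. The schedule of activities and its permitted visit windows are redacted, so visit timing is an assumption. SAP 5.6.8 and 5.6.9 place both exams at each visit; I assume they are also done at early exit. The plan states no figure of its own to reproduce here.

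**Rule.** Let *d* be the day of the extra exam, *s* the day of the scheduled exam in the same window, and *t* the target day. The extra exam is dropped if |s − t| < |d − t|, or if the distances are equal and s is later than d.

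**Early exit, earlier visits on target (s = t).** The scheduled exam has distance 0, so any later exit exam in that window loses. An exit before the target day stands alone in its window and is kept.

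| Window | Target | Exit days kept | Exit days dropped |
|---|---|---|---|
| 2 to 4 | 3 | 2 (1 day) | 4 (1 day) |
| 5 to 10 | 7 | 5 to 6 (2 days) | 8 to 10 (3 days) |
| 11 to 21 | 14 | 11 to 13 (3 days) | 15 to 21 (7 days) |
| 22 to 45 | 30 | 22 to 29 (8 days) | none before Day 30 |
| Total | | 14 | 11 |

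Non-visit days from 2 to 29: 28 − 3 = 25. Dropped: 11/25 = 44%.

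Protocol 7.1 encourages participants who stop treatment to return for safety assessments at Day 30. If someone has an exam on stopping in Days 22 to 29 and also attends Day 30, that exam loses too: 11 + 8 = 19, and 19/25 = 76%.

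**Early exit, visits off target.** I shifted each visit uniformly around its target, from up to ±1 day for every visit to up to ±1, ±2, ±3 and ±7 days for Days 3, 7, 14 and 30 (100,000 draws per setting). Exit exams were placed evenly over non-visit days. Between 29.8% and 36.1% were dropped.

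**Unscheduled exams, all visits attended.** With visits on target, every non-visit day from 2 to 45 loses: 44 − 4 = 40, and 40/40 are dropped. With the same off-target settings, exams placed up to the last visit were dropped in 64.2% to 86.6% of draws. This treats an unscheduled exam as competing within its window. If SAP 6.5.1 is instead read as covering only follow-up and exit visits, the by-visit tables have no specified place for such exams.

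**The case against.** The strongest reply is that harm is reported elsewhere. A participant who exits because of an eye problem should have an AE leading to discontinuation. SAP 5.6.2 tabulates and lists those events, and the windows do not touch them. A supplemental exam under Protocol 8.3.3 follows an AE already reported. This stands, and it rules out the stronger inference that the safety signal itself is lost. It does not cover everything: the biomicroscopy criterion is a fixed grade change, while AE reporting depends on the investigator's judgment. A qualifying worsening or an IOP rise not reported as an AE could be missing from both places.

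Second, SAP Section 1 puts table and listing specifications in a separate document, and parts of the SAP are not visible. The shells may list every exam. That also stands, so the claim is limited to the summaries the visible SAP specifies; the data remain in the database.

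Third, the rule is a routine convention and already applies only to by-visit analyses, so an any-time table would not be bound by it. Agreed: the gap is the absence of such a table, not the rule.

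A reader might also infer that the active arm loses more exams through AE-driven exits. The documents give no basis for that. The nearest text, Protocol 2.2, says only that Phase 2 discontinuation rates were generally low.

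**Conclusion.** The point holds for the specified by-visit summaries. Early-exit exams that follow a scheduled visit in the same window do not enter the IOP and biomicroscopy tables: 44% of non-visit exit days if earlier visits are on target, and about 30% to 36% if they are not. For participants who attend every visit, about 64% to 100% of unscheduled exams do not enter.

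These percentages give every day equal weight and rest on assumed visit timing. They are shares of days, not of participants. The documents state no exit rate and no count of unscheduled exams, and some exits, such as loss to follow-up, may yield no exam. The number of participants affected is therefore unknown. It would be wrong to read the rule as always keeping the earlier, calmer exam: on 14 of the 25 days the exit exam is kept, and ties go to the later exam. This is a worthwhile gap to close in safety reporting, and it does not affect the efficacy conclusions.

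**What to change.** Keep the nearest-day rule in SAP 6.5.1 for by-visit tables. Add one any-post-baseline row to each of two sections, using all post-dose exams including early-exit and unscheduled ones:

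- SAP 5.6.8: each participant's maximum IOP increase from baseline in either eye, summarized by treatment group.
- SAP 5.6.9: the number and percentage of participants with a clinically significant biomicroscopy finding at any time after the first dose.

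Under these rows none of the exams counted above is lost: 0 of 25 exit days and 0 of 40 unscheduled days, against 11 and 40 now with visits on target. The cost is a few SAP lines and table rows from data already collected, with no change to trial conduct. Participants examined more often have more chances of an extreme value, so the rows should be read descriptively beside the by-visit tables. Vital signs (SAP 5.6.3) are also summarized only by timepoint; extending the same row to them is optional.

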### 6.5.2. Missing Date of the Last Dose of Study Intervention

When the date of the last dose of study intervention is missing for a participant in the safety population, all efforts should be made to obtain the date from the investigator. If the data is still missing after all efforts have been made, the last available dosing record date will be used as the last dose date.

### 6.5.3. Missing Severity Assessment for Adverse Events

If severity is missing for an AE that started before the date of the first dose of study intervention, an intensity of mild will be assigned. If the severity of a TEAE is missing, the maximum severity will be assigned to the event for the summarization by severity. The value will be displayed as missing in the data listing.

### 6.5.4. Missing Causal Relationship to Study Drug for Adverse Events

If the relationship to the study intervention is missing for a TEAE, the event will be considered related to the study intervention for the summarization. The value will be displayed as missing in the data listing.

### 6.5.5. Missing Date Information for Adverse Events

The following imputation rules only apply to cases in which the start date for AEs is incomplete (i.e., partly missing):

#### Missing month and day

- If the year of the incomplete start date is the same as the year of the first dose of study intervention, the month and day of the first dose of study intervention will be assigned to the missing fields.

AGN-190584

- If the year of the incomplete start date is before the year of the first dose of study intervention, *December 31* will be assigned to the missing fields.
- If the year of the incomplete start date is after the year of the first dose of study intervention, *January 1* will be assigned to the missing fields.

#### **Missing month only**

- If only the month is missing, the day will be treated as missing and both the month and the day will be replaced according to the above procedure.

#### **Missing day only**

- If the month and year of the incomplete start date are the same as the month and year of the first dose of study intervention, the day of the first dose of study intervention will be assigned to the missing day.
- If either the year of the incomplete start date is before the year of the date of the first dose of study intervention or if both years are the same but the month of the incomplete start date is before the month of the date of the first dose of study intervention, the last day of the month will be assigned to the missing day.
- If either the year of the incomplete start date is after the year of the date of the first dose of study intervention or if both years are the same but the month of the incomplete start date is after the month of the date of the first dose of study intervention, the first day of the month will be assigned to the missing day.

If the stop date is complete and the imputed start date as above is after the stop date, the start date will be imputed by the stop date.

If the start date is completely missing and the stop date is complete, the following algorithm will be used to impute the start date:

- If the stop date is after the date of the first dose of study intervention, the date of the first dose of study intervention will be assigned to the missing start date.
- If the stop date is before the date of the first dose of study intervention, the stop date will be assigned to the missing start date.

AGN-190584

**6.5.6. Missing Date Information for Prior or Concomitant Medications**

For prior or concomitant medications, including rescue medications, incomplete (i.e., partly missing) start dates and/or stop dates will be imputed. When the start date and the stop date are both incomplete for a participant, the start date will be imputed first.

**6.5.6.1. Incomplete Start Date**

The following rules will be applied to impute the missing numeric fields for an incomplete prior or concomitant medication start date. If the stop date is complete (or imputed) and the imputed start date is after the stop date, the start date will be imputed using the stop date.

**Missing month and day**

- If the year of the incomplete start date is the same as the year of the first dose of study intervention, the month and day of the first dose of study intervention will be assigned to the missing fields.
- If the year of the incomplete start date is before the year of the first dose of study intervention, *December 31* will be assigned to the missing fields.
- If the year of the incomplete start date is after the year of the first dose of study intervention, *January 1* will be assigned to the missing fields.

**Missing month only**

- If only the month is missing, the day will be treated as missing and both the month and the day will be replaced according to the above procedure.

**Missing day only**

- If the month and year of the incomplete start date are the same as the month and year of the first dose of study intervention, the day of the first dose of study intervention will be assigned to the missing day.
- If either the year of the incomplete start date is before the year of the date of the first dose of study intervention or if both years are the same but the month of the incomplete start date is before the month of the date of the first dose of study intervention, the last day of the month will be assigned to the missing day.
- If either the year of the incomplete start date is after the year of the date of the first dose of study intervention or if both years are the same but the month of the incomplete start date is after the month of the date of the first dose of study intervention, the first day of the month will be assigned to the missing day.

AGN-190584

**6.5.6.2. Incomplete Stop Date**

The following rules will be applied to impute the missing numeric fields for an incomplete prior or concomitant medication stop date. If the date of the last dose of study intervention is missing, impute it as described in [Section 6.5.3](#). If the imputed stop date is before the start date (imputed or non-imputed start date), the imputed stop date will be equal to the start date.

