6.5.1. Prohibited Interventions and Washout Before the Study

Use of medications that may have a substantial effect on visual function or the optical properties of the eye is prohibited 2 weeks prior to Day 1 visit and during the study:

- systemic medications with potential ocular side effects, including topiramate, hydroxychloroquine, ethambutol, phosphodiesterase 5 inhibitors (sildenafil, vardenafil, tadalafil), or tamoxifen
- ophthalmic, systemic, or intranasal anticholinergics and α -adrenergic receptor agonists with potential pupillary or accommodative effects, including oxymetazoline, pilocarpine, tetrahydrozoline, phenylephrine, naphazoline, cyclopentolate, atropine, beta-blockers, or antihistamines
- systemic maprotiline, tricyclic antidepressants, or monoamine oxidase inhibitors

AGN-190584

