#### **6.3.6. Prior/Concomitant medications**

*Prior medication* is defined as any medications taken prior to the start of study intervention.

*Concomitant medication* is defined as any medication taken on or after the start of study intervention regardless of the start date of the medication.

The number and percentage of participants with prior and concomitant medication use will be summarized by treatment group and Anatomical Therapeutic Chemical code for the safety population. If a participant took a specific medication multiple times or took multiple medications within the same therapeutic class, the participant will be counted only once for the coded drug name or therapeutic class. Formulations (including salts, esters, etc.) containing the same active ingredient will be pooled under the coded drug name of the base compound. Medications containing multiple active ingredients of different coded drug names will be

AGN-190584

reviewed during the course of the study and may be pooled under a single coded drug name for analyses. No statistical comparisons will be performed.

AGN-190584

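### SAP 6.5.6.1 and 6.5.6.2 correct the same date conflict in opposite directions, so one pattern of partial dates turns a medicine stopped before dosing into a concomitant one

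*SAP*

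**What the plan says.** SAP 6.5.6 sets the order: "When the start date and the stop date are both incomplete for a participant, the start date will be imputed first".

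SAP 6.5.6.1 covers the start date. Its correction applies under this condition: "If the stop date is complete (or imputed) and the imputed start date is after the stop date". The start is then moved to the stop.

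SAP 6.5.6.2 covers the stop date. Its correction, with its condition, reads: "imputed stop date is before the start date (imputed or non-imputed start date), the imputed stop date will be equal to the start date".

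SAP 6.3.6 decides how the result is tabulated. A prior medication is one taken before the start of study intervention. A concomitant medication is "any medication taken on or after the start of study intervention regardless of the start date of the medication".

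For a missing last-dose date, SAP 6.5.6.2 points to 6.5.3. That section deals with missing severity of adverse events; the last-dose rule is in 6.5.2.

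**The concern.** One and the same situation, an imputed stop earlier than an imputed start, is named by both rules. One moves the start, the other moves the stop. Nothing says which prevails except the order of imputation, and that order leads to the correction that can discard recorded information.

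In the affected pattern the start is a placeholder: only the year is known, and the first-dose date fills in the rest. The stop carries a recorded month. The plan keeps the placeholder and overwrites the recorded month. A medicine that ended before dosing then appears in the concomitant table and drops out of the prior table.

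The prior/concomitant boundary has some relevance here. Protocol 6.5.1 says that use of medicines with a substantial effect on visual function or the eye's optics "is prohibited 2 weeks prior to Day 1 visit and during the study". Some stops shortly before Day 1 are therefore to be expected.

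**Working it through.** The plan gives no figure to reproduce. The check is date logic.

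**Inputs**
- Start rules (SAP 6.5.6.1), reference = first dose. Year only, same year: the first-dose date. Year only, earlier year: 31 December. Day missing, earlier month: last day of that month.
- Stop rules (SAP 6.5.6.2): the same scheme, reference = last dose.
- Classification (SAP 6.3.6): concomitant if the medicine was taken on or after the first dose.
- Assumption for illustration: first dose 15 Jul 2020, last dose 13 Aug 2020 (29 days later, so 30 dosing days).

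**Case A: start recorded as 2020, stop recorded as Jun 2020**
1. Start is imputed first: 15 Jul 2020.
2. Stop: June precedes the last-dose month, so 30 Jun 2020.
3. 30 Jun is before 15 Jul, so the two dates conflict.
4. Under 6.5.6.2 the stop becomes 15 Jul. The record reads 15 Jul to 15 Jul: concomitant, and not prior.
5. Under 6.5.6.1 the start would become 30 Jun. The record would read 30 Jun to 30 Jun: prior only.

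At step 1 no imputed stop exists yet. The "If the stop date is complete (or imputed" condition therefore cannot act on an imputed stop in a single pass, and step 4 is what the stated order produces.

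**Case B: same start, stop recorded in full as 20 Jun 2020**

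Only the start is imputed. By 6.5.6.1, when the "imputed start date is after the stop date, the start date will be imputed using the stop date", which gives 20 Jun to 20 Jun: prior only. Losing only the day of the stop date reverses the classification.

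**Scope**

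Take all feasible pairs of partial dates (year only, or month and year) in the first-dose year and the year before, with first dose 15 Jun 2020 and last dose 14 Jul 2020. There are 375 pairs, of which 21 conflict:
- 5: start year-only in the first-dose year, stop month January to May of that year. Switched from prior to concomitant.
- 11: start year-only in the year before, stop month January to November of that year. The stop month is overwritten with 31 December, but the medicine stays prior.
- 5: start month after the last dose, stop year-only. Concomitant under either rule.

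5 + 11 + 5 = 21. For a first dose in calendar month m, the number of switched patterns is m − 1: 5 for June, 2 for a first dose on 20 March, 0 for 15 January.

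**When the start month is recorded and precedes dosing**

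The start becomes the last day of its month. A stop in the same or a later month before dosing becomes the last day of that month, so the stop cannot precede the start. Over all 366 first-dose dates in 2020, the pairs with a recorded start month and a stop month before the first-dose month number Σ days(m) × m(m − 1)/2 = 8752. None becomes concomitant. The year-only starts number Σ days(m) × (m − 1) = 2018, and all of them do. That second result holds by construction, because those pairs are exactly the triggering pattern.

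**The case against.** **The order settles it.** SAP 6.5.6 says start first, so a programmer in a single pass reaches one answer and the mention of an imputed stop in 6.5.6.1 is redundant. This largely stands as a point about reproducibility, although a programmer who applies 6.5.6.1 after imputing both dates gets the other answer. It does not help with the result itself: the determinate answer contradicts the recorded stop month.

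**The effect is small.** This stands. SAP 6.3.6 plans no between-group comparison of medications, and nothing in the efficacy analyses uses these dates.

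**Washout.** A reader might infer that compliant washouts will generally show up as prohibited use on treatment. The documents do not support that. Protocol 6.5.2 requires start and end dates to be recorded. A medicine begun in an earlier year gets a start no later than 31 December of that year and is not switched. One stopped in the first-dose month with the day missing is concomitant under either correction, so the conflict is not the cause. Prohibited use is also reported by site staff to the sponsor (Protocol 6.5), and significant deviations are summarized separately (SAP 6.3.3).

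**Adverse events.** A reader might infer that treatment-emergent counts are wrong in the same way. SAP 6.5.5 contains no contradiction, only a gap: its repair starts "If the stop date is complete and the imputed start date as above is after the stop date", so a partial stop does not trigger it. An adverse event with start 2020 and stop Jun 2020 would keep an imputed onset on the first-dose date. Whether it then counts as treatment-emergent is unclear. Protocol 9.4.2.1 includes onset on the date of first dose; SAP 5.6.2 requires onset after the first administration. Adverse events are collected from consent and screening lasts at most 30 days, so an unknown onset month should be rare.

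**Conclusion.** The contradiction is real, and in the stated order the rule that applies can overwrite recorded data. A medicine is switched from prior to concomitant only when its start has no month and lies in the first-dose year, and its recorded stop month is earlier in that year.

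It would be wrong to conclude that any pair of partial dates is affected, or to read 2018 of 2018 as a frequency. It counts calendar combinations chosen to meet the trigger. The documents do not say how many such records exist; few are likely. The illustrative dates in 2020 and the 30-day dosing interval are assumptions, but the logic does not depend on them beyond the month of first dose.

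This is a minor point, confined to the descriptive medication tables and worth correcting because correction is cheap.

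**What to change.** Replace the two opposing corrections in SAP 6.5.6 with one rule, applied after both dates have been imputed:

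> If both dates are incomplete and the imputed stop date is before the imputed start date, the date with fewer recorded fields is set to the other; a recorded month or year is never overwritten. If the start date is complete, an earlier imputed stop date is set to the start date. If the stop date is complete, a later imputed start date is set to the stop date.

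The last sentence keeps what 6.5.6.1 already does for complete stops. In all 21 conflicting patterns above, one date has a month and the other only a year, so the rule never meets a tie. The 5 switched patterns become prior, the 11 keep their stop month, and the 5 with a start after the last dose keep their start month.

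Correct the pointer in 6.5.6.2 for a missing last-dose date from 6.5.3 to 6.5.2.

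Optionally, close the gap in 6.5.5 while keeping its existing condition:

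> If the imputed start date is after the stop date, or after the last day of the recorded stop month or year, and moving it overwrites no recorded month or year, the start date is set to the stop date (or that last day).

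Cost: a few sentences and a small change to the date-imputation program before database lock, with no new data. The downside is that a few records move from concomitant to prior or, with the optional change, from treatment-emergent to pre-treatment, so those counts may fall slightly.
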